12.1.7 Missing Efficacy Data Imputations

Lesion Count Variable Missing Data Imputation

Missing 12 week data will be estimated by multiple imputation and subsequently analyzed. Missing lesion count data will be derived for the analysis using the method of Markov Chain Monte Carlo (MCMC) multiple imputation which does not rely on the assumption of data missing at random. Additionally, the pattern of missing observations in each treatment group cannot influence the missing value estimation in the other because the imputation is being conducted independently for each treatment group.

Multiple imputation and subsequent analysis will involve 4 distinct phases with these principal tasks:

1. Calculate the number of missing values to be estimated by MCMC (nmiss) for 12 week value.
2. Create a data set of subjects, one for each treatment group, with observed values and those needing estimation by MCMC. The missing lesion count values in each data set will be filled in using the MCMC method ‘5 x nmiss’ times to generate ‘5 x nmiss’ data sets. The resulting data sets for each treatment arm will be combined into one complete data set for each imputation.
3. For each complete data set, the absolute change in lesion counts for baseline minus the 12 week value will be computed. Each complete data set will be analyzed as specified for the particular analysis.
4. The results from these analyses will be combined into a single inference using SAS PROC MIANALYZE.

EGSS Missing Data Imputation

A similar procedure will be used for the analyses based on proportion of EGSS successes wherein the ANCOVA analysis is replaced with a logistic regression analysis. Specifically, missing 12 week EGSS values from which the dichotomized EGSS is derived will be estimated by (MCMC) which does not rely on the assumption of data missing at random. Additionally, the

pattern of missing observations in each treatment group cannot influence the missing value estimation in the other because the imputation is being conducted independently for each treatment group.

The missing 12 week EGSS values will be derived for the analysis using the method of Markov Chain Monte Carlo (MCMC) multiple imputation. Multiple imputation and subsequent analysis will involve 4 principal tasks:

1. Calculate the number of missing values to be estimated by MCMC (nmiss) for 12 week value.

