8.3 Subject Withdrawal Criteria

Reasons for withdrawal may include, but are not limited to, the following:

- Acne flare, as determined by the investigator, which requires treatment with a disallowed therapy.
- Either at the investigator's request, for tolerability reasons (eg, severe adverse reactions), or at the subject's request.
- When the requirements of the protocol are not followed.
- When a concomitant therapy likely to interfere with the results of the study is reported, or required by the subject (the investigators will report all such information

on the source documents/case report forms (CRFs) and decide, in accordance with the sponsor, whether the subject is to be withdrawn).

- When a subject is lost to follow-up. The investigators will try twice to reach the subject by telephone and will send a follow-up letter by certified mail before considering that the subject is lost to follow-up. These actions will be reported on the End of Study CRF and a copy of the follow-up letter maintained in the investigator's file.

All premature discontinuations and their reasons must be carefully documented by the investigator on the final CRF, and, if need be, on the AE form. In any case, no subject who has been included and has a study number assigned can be replaced by another if they discontinue prematurely for whatever reason. All data gathered on the subject prior to termination will be made available to the sponsor.

Reasons for study completion/discontinuation as listed on the final report form are defined as follows:

Normal Study Completion – Subject completes the study as planned in the protocol.

Adverse Event – Complete AE form.

Death – Complete SAE form.

Subject Request – Consent withdrawal, subject moved, schedule conflicts.

Protocol Violation – Contact the Sponsor or designee before making decision.

Lost to Follow-Up – Document with 2 phone calls and a certified letter.

Pregnancy – Subject will discontinue study drug immediately, but will be followed to term. Complete pregnancy and SAE forms.

Worsening Condition – Subject requires alternate treatment for acne before the end of the study and the investigator determines it is not due to lack of efficacy.

Lack of Efficacy – Subject requires alternate treatment for acne after at least 2 weeks of study drug treatment and the risk of continuing the subject in the study outweighs the benefit as determined by the investigator.

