9.1 Methods of Assigning Subjects to Treatment Groups

This is a double-blinded study, in which the identity of the study drug will be unknown to investigator/evaluator and subjects, as well as all individuals closely associated with the study.

Subjects will be randomized to 1 of the 2 study drug groups in a ratio of 1:1 (IDP-121 [tretinoin 0.05%] Lotion : IDP-121 Vehicle Lotion). Each screened subject will be assigned a unique 6-digit study subject number assigned by the investigational center, which will consist of the 3-digit investigational center/site number (pre-assigned by sponsor/designee) and the 3 digit chronological screening order number, starting with 001 (eg, 101001, 101002). The study drug kit will be assigned to subjects based on a randomization code and kit will be dispensed to the subjects at Baseline by the IRW system, and at Week 4 and Week 8 visits. A study drug log will document the inventory and dispensing of study drug at each investigational center.

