11.2 Evaluation of Efficacy

The determination of efficacy will be based on evaluator-blinded assessments of the signs and symptoms of acne vulgaris. Evaluators must be a board-certified/board-eligible dermatologist or have appropriate documented experience and training, and be present for formal study training and validation at the Investigator Meeting (and/or Site Initiation Visit), or obtain a waiver from the Sponsor based on experience (or through additional training organized by the Sponsor).

The EGSS scores and lesion counts will be performed at each study visit. The EGSS scores will be collected *before* the Lesion Counts. All Subject assessments will be performed by a trained and validated Evaluator. Every effort should be made to have the same evaluator assess the same Subject at each visit. If this is not possible, the same Evaluator must assess the Subject at both the baseline and Week 12 visits.

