11.4.8 Pregnancy

All female subjects of childbearing potential must use an effective method of birth control during the course of the study, in a manner such that risk of contraceptive failure is minimized. Abstinence is allowed as a birth control method.

Before enrolling a female subject of childbearing potential in this clinical trial, the investigator must review the following information about study participation:

- Informed consent requirements
- Contraceptives in current use

Following review of this information and appropriate subject counseling, the investigator or designee and the subject must sign the informed consent before study enrollment.

During the study, all female subjects of childbearing potential should be instructed to contact the investigator immediately if they suspect they might be pregnant (eg, missed or late menstrual period).

If a subject or investigator suspects that the subject may be pregnant prior to study enrollment, the study drug must be withheld until the results of laboratory pregnancy testing are available. If pregnancy is confirmed, the subject must not receive study drug and must not be enrolled in the study. If pregnancy is suspected while the subject is receiving study treatment, the study drug must immediately be withheld until the result of pregnancy testing is known. If pregnancy is confirmed, the study drug will be permanently discontinued and the subject will be followed until the pregnancy comes to term. A Pregnancy Report form will be submitted to the sponsor, initially and at the end of the pregnancy, which includes the outcome of the pregnancy and any complications occurring during the pregnancy or the delivery.

All confirmed pregnancies must be immediately reported to the medical monitor within 24 hours of the investigator's awareness of the pregnancy. All confirmed pregnancies must be reported via confirmed facsimile/email transmission and must be submitted on a SAE and pregnancy report forms within 24 hours of the investigator's awareness of the pregnancy using the same reporting as procedure for an SAE under Section 11.4.6.

12 Statistics

All statistical processing will be performed using SAS® version 9.3 or later unless otherwise stated. Statistical significance will be based on two-tailed tests of the null hypothesis resulting in p-values of 0.05 or less.

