A similar procedure will be used for the analyses based on proportion of EGSS successes wherein the ANCOVA analysis is replaced with a logistic regression analysis. Specifically, missing 12 week EGSS values from which the dichotomized EGSS is derived will be estimated by (MCMC) which does not rely on the assumption of data missing at random. Additionally, the pattern of missing observations in each treatment group cannot influence the missing value estimation in the other because the imputation is being conducted independently for each treatment group.

The missing 12 week EGSS values will be derived for the analysis using the method of Markov Chain Monte Carlo (MCMC) multiple imputation. Multiple imputation and subsequent analysis will involve 4 principal tasks:

1. Calculate the number of missing values to be estimated by MCMC (nmiss) for 12 week value.
2. Create a data set, one for each treatment group, of subjects with observed values and those needing estimation by MCMC. The missing EGSS values in each data set will be filled in using the MCMC method ‘5 x nmiss’ times to generate ‘5 x nmiss’ data sets. The resulting data sets for each treatment arm will be combined into one complete data set by imputation.

Syntax:

```
proc mi data=datain out=dataout seed=&seed. nimpute=5xnmiss <options>;
  where trtpn=(1, or 2);
  mcmc chain=multiple;
  var baseline week4 week8 week12;
```

run;

3. For each complete data set, the dichotomous success rate (clear or almost clear with a 2-point change from baseline) will be computed. The 12-week estimated global values will be rounded to the nearest integer value prior to evaluating the success rate. Each complete data set will be analyzed with a logistic regression with factors of treatment group and analysis center.
4. The results from these analyses will be combined into a single inference using SAS PROC MIANALYZE.

A total of 2 random seeds will be needed to impute EGSS for the two treatment groups. Those 2 random seeds have been pre-specified by using a random number generator:

- EGSS; IDP-121 Lotion: Seed= 1210644108
- EGSS; IDP-121 Vehicle: Seed= 763715437

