12.8.2 Sample Size Determination

These power calculations are based primarily on the observed Week 12 results of the Study 2 in Atralin™ (tretinoin) Gel, 0.05% NDA 022070 application. This study was a two-arm trial of Atralin™ versus its vehicle and is felt to be a relevant study in NDA 022070 for powering the current study. The next three power calculations are constructed from the results of Study 2.

A sample size of 400 per treatment arm has at least 96% power to detect a statistically significant difference with a significance level of 0.05. The estimated absolute change from baseline in

treatment means were 6.5 and 3.5 for Atralin™ versus its vehicle, respectively, with a standard deviation of 11.3.

A sample size of 400 per treatment arm has greater than 99% power to detect a statistically significant difference with a significance level of 0.05 using the estimated absolute change from baseline in treatment means of 17.8 and 9.9 for Atralin™ versus its vehicle, respectively, with a standard deviation of 24.7.

The sample size estimates for the dichotomized EGSS require a substantially larger enrollment in order to achieve a power of at least 90%. The success rates observed in the second Atralin™ study was 23% for Atralin™ and 14% for its vehicle which is a difference of 9%. Approximately 90% power is achieved with sample sizes of 400 per treatment group, respectively, using a 1:1 randomization.

It is noted that the same differential in success rates was observed in Study 1 (Atralin™ (tretinoin) Gel, 0.05% NDA 022070 application). The success rates observed in the first Atralin™ study was 13% for Atralin™ and 4% for its vehicle which is also a difference of 9%. Using these estimates, more than 99% percent power is achieved with sample sizes of 400 per treatment group.

The clinical study will be conducted under a common protocol at each investigational site and every effort will be made to promote consistency in study execution at each investigational site as well as uniform evaluation of the EGSS evaluation for subjects at the various study visits. The experience in clinical trial execution gained during the execution of several acne studies conducted under the guidance of the Sponsor raises the expectation that the differential between the success rates of the two arms will be greater than 9%. Thus, the power of the EGSS is expected to be at least 95% for sample sizes of 400 subjects in each arm.

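### Missing Week 12 EGSS is imputed from EGSS history alone; adding the lesion counts from the same visits would reduce a bias that can arise if count-related dropout differs between arms

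*Combined protocol and SAP*

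**What the plan says.** Amendment 3, Section 12.1.8 (EGSS part) states that "missing 12 week EGSS values from which the dichotomized EGSS is derived will be estimated by (MCMC", run independently in each treatment group. The PROC MI code printed there has the variable list "var baseline week4 week8 week12". Lesion counts have their own runs and seeds, so for EGSS these four variables are the EGSS grades. Imputed grades are rounded to an integer, success is derived, and a logistic regression on treatment and analysis center is combined over imputations. The text adds that the method does not need the data to be missing at random. (Section 12.1.7 of the original protocol has the same sentence but no variable list.)

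Section 11.2: "The EGSS scores and lesion counts will be performed at each study visit".

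Section 12.1.9 gives two EGSS sensitivity analyses. One is a GEE on observed data with treatment, center and visit. The other is a logistic multiple imputation on treatment and center only. Neither contains lesion counts.

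Section 8.3 lists, among the reasons for withdrawal, "Acne flare, as determined by the investigator, which requires treatment with a disallowed therapy"; lack of efficacy and tolerability are also named.

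**The concern.** The variable list is the missing-data assumption. Imputing by arm makes the assumption conditional on arm; it does not remove it. MCMC copes with an arbitrary pattern of gaps, but that is not the same as an arbitrary mechanism.

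Baseline EGSS can only be 3 or 4, and later grades sit on a five-level scale. The counts are a finer measure of the same disease. Two subjects with the same grade but different counts may differ both in their chance of leaving and in their chance of success at Week 12. If so, imputing from grades alone gives the leavers the wrong success rate.

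All three co-primaries must succeed, and on the main planning inputs EGSS has the least power to spare. Different mechanisms in the two arms are conceivable: flare or lack of effect on vehicle, irritation on active (the Introduction notes irritation as a limit of topical retinoids).

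**Working it through.** **1. The plan's own power.** Inputs: "Statistical significance will be based on two-tailed tests of the null hypothesis resulting in p-values of 0.05 or less" (Section 12); "Subjects will be randomized to 1 of the 2 study drug groups in a ratio of 1:1" (Section 9.1); the planning "study was 23% for Atralin™ and 14% for its vehicle which is a difference of 9" points, and "Approximately 90% power is achieved with sample sizes of 400 per treatment group" (both Section 12.8.2).

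Pooled p = (0.23 + 0.14)/2 = 0.185.
SE under the null = √(2 × 0.185 × 0.815/400) = 0.02746.
SE under the alternative = √((0.23 × 0.77 + 0.14 × 0.86)/400) = 0.02727.
Power = Φ[(0.09 − 1.96 × 0.02746)/0.02727] = Φ(1.33) = 90.8%. This reproduces the stated figure.

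Lesion counts, with power = Φ[δ/(SD√(2/400)) − 1.96]:
- δ = 3.0, SD 11.3: Φ(3.755 − 1.96) = 96.4%.
- δ = 7.9, SD 24.7: Φ(4.523 − 1.96) = 99.5%.

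EGSS is therefore the lowest-powered co-primary on the Study 2 inputs. On the Study 1 rates (13% vs 4%) its power is 99.6%, and it is not.

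**2. How the bias arises.** Let m be the missing fraction in an arm and d the imputed minus the true success rate among those missing. The arm bias is m·d, and the bias in the difference is m_A·d_A − m_V·d_V. Similar mechanisms nearly cancel; different ones do not. Two simulated cases with imputation from EGSS only:
- Shared count-driven mechanism, missing 13.1% on active and 16.9% on vehicle: arm biases +0.73 and +0.85 points (d = 0.73/0.131 = 5.6 and 0.85/0.169 = 5.0). Difference −0.12. With counts added: +0.09, +0.19, −0.10.
- Vehicle only, 20% missing: arm biases −0.03 and +0.78 (d_V = 0.78/0.20 = 3.9). Difference −0.81. With counts added: −0.01, +0.20, −0.21.

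**3. Range.** The documents state no dropout rate or mechanism, so everything here is assumed.

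Simulation 1: a latent severity drives EGSS (23% vs 14%) and both counts. Dropout after Week 4 or 8 is 10-20%, with log-odds slopes of 1-2 per SD of count, and the EGSS/count correlation is 0.45-0.67. Bias comes from 300,000-400,000 subjects per arm. Power comes from 800 trials of 400 per arm at 15% dropout, using Rubin's rules on the log odds ratio without a center term.

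Simulation 2: about 22% vs 14%, 12-15% missing, 700 trials, log counts.

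| Dropout depends on | Bias in difference, EGSS only (points) | With counts | Power, EGSS only → with counts |
|---|---|---|---|
| Nothing (random) | −0.2 (20% missing) | −0.2 | 84.5% → 83.8% |
| EGSS only | −0.1 (20% missing) | −0.2 | 84% → 84% (Sim. 2) |
| Counts, same in both arms | +0.1 and +0.3 (20%, slopes 1 and 2) | −0.2 and −0.1 | 86% → 86% |
| Counts, vehicle only | −0.4 to −0.9 | −0.1 to −0.2 | 79% → 85%; Sim. 2: 78% → 86% |

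In Simulation 2 the vehicle-only estimate was 8.0 points against a true 8.6, and 8.6 with counts. With a shared mechanism its bias fell from about +0.3 to +0.1. The Monte Carlo SE of a power near 80% is √(0.8 × 0.2/800) = 1.4 points. Under a shared mechanism, Simulation 1 overstated each arm's success rate by about 0.4-1.7 points, falling to at most about 0.3 with counts.

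**4. Limit of the remedy.** The cases above let dropout depend on counts already observed. Two further large-sample checks of the vehicle-only case compared this with dropout driven by the count at the missed visit:
- 600,000 per arm, 8-16% missing: earlier counts, −0.4 to about −0.1 (raw or log counts alike); missed-visit count, −1.0 to only about −0.9.
- 400,000 per arm, about 14% missing: earlier counts, −0.6 to about −0.2; missed-visit count, −0.9 to −0.6 (slope 1) and −1.1 to −0.8 (slope 1.5).

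**The case against.** The strongest reply is that the co-primary is a between-arm comparison, and a shared mechanism leaves it almost untouched. This stands, and the point is conditional for that reason.

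Second, flare and lack of efficacy may well develop after the last completed visit. Recorded counts recover little of that (step 4). This stands too.

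Third, subjects who leave before Week 4 gain only baseline counts, which eligibility restricts to 20-40 and 20-100. For them the gain is small.

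Fourth, early terminators are asked to complete the Week 12 assessments before other therapy if possible (Sections 7.1 and 8.3). True missingness may therefore be below the assumed range, although the statistics section does not say how those values enter the Week 12 analysis.

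Fifth, Section 12 refers to a separate SAP, and the printed syntax has an options placeholder. A wider list elsewhere cannot be excluded. The protocol code would still need to agree with it.

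None of this gives a reason to leave the counts out. Random and EGSS-driven dropout showed no material loss from including them.

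**Conclusion.** The omission is real, and including the counts is a cheap improvement. The plan's statement that no missing-at-random assumption is needed is wrong for the step as coded. Arm success rates can be biased if dropout depends on lesion counts. The treatment difference is affected materially only if that dependence differs by arm: about 0.4-0.9 points if only vehicle is affected, at most about 0.3 points with a common mechanism, and nothing of note if dropout follows EGSS alone. These sizes rest on assumed missingness of 8-20% and assumed latent models.

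A reader might infer that the co-primary is biased as planned. The documents do not support that, because they give neither a dropout rate nor a mechanism. A reader might also infer a threat to type I error. In a stress case with count-driven dropout running in opposite directions in the two arms, Simulation 1 gave bias of 0.9-4.0 points and, for one null pattern at 15% dropout, a rejection rate of about 7.4% (3.8% with counts; Monte Carlo SE about 0.8). Nothing in the documents indicates such a pattern. Nor can one say that the counts would remove the bias: worsening unseen at the last visit stays largely uncorrected.

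**What to change.** In the EGSS code of Amendment 3 Section 12.1.8 (and in the SAP), extend the by-arm VAR statement to 12 variables: EGSS, inflammatory count and non-inflammatory count, each at baseline and Weeks 4, 8 and 12. State whether counts enter raw or log-transformed; if they are skewed, log(count + 1) allows for zeros. Replace the missing-at-random sentence with one saying that the imputation assumes missingness at random within arm given these variables.

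Leave the two lesion-count imputations and their seeds unchanged. No deficiency has been shown there, so a joint re-imputation of all three co-primaries is not needed.

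Cost: no new data; a larger model (12 instead of 4 variables, about 400 subjects per arm); and a documented change before unblinding to syntax that the Amendment 2 summary says was added on the agency's recommendation. Dropout driven by unobserved worsening is outside the reach of this change.

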12.1.8 Sensitivity Efficacy Analyses

Sensitivity analyses for absolute change in lesion count

The first sensitivity analysis for absolute change in lesion count use a repeated measures ANCOVA, with treatment, analysis center, and visit (ie, Week 4, Week 8) as independent factors and a covariate of baseline lesion count. In this analysis, data from all post-baseline visits will be included with no imputation for missing data.

The second sensitivity analysis will use the model based multiple imputation method to impute missing data for the absolute change in lesion counts at Week 12. Multiple imputation will involve 4 principal tasks:

1. Calculate the number of missing values (nmiss) for absolute change in lesion count.
2. Missing values will be filled in ‘5 x nmiss’ times to generate ‘5 x nmiss’ complete data sets. The imputation model used will be an ANCOVA with factors of treatment group and analysis center, and a covariate of baseline lesion count (ie, the imputation model will be the same as the analysis model). Appropriate modifications will be made should the analysis be based on a non-parameteric method.

3. Each complete data set will be analyzed with an ANCOVA with factors of treatment group, and analysis center, and a covariate of baseline lesion count.
4. Results from these analyses will be combined into a single inference.

Sensitivity analyses for EGSS

The first sensitivity analysis for the dichotomized EGSS success will use a repeated measures logistic regression model (generalized estimating equations), with dichotomized EGSS success as the dependent variable and treatment, analysis center, and visit (ie, Week 4, Week 8) as independent factors. In this analysis, data from all post-baseline visits will be included with no imputation for missing data.

The second sensitivity analysis will use the model based multiple imputation method to impute missing data for the dichotomized EGSS data. Multiple imputation will involve 4 principal tasks:

1. Calculate the number of missing values (nmiss) for absolute change in lesion count.
2. Missing values will be filled in ‘5 x nmiss’ times to generate ‘5 x nmiss’ complete data sets. The imputation model used logistic regression with factors of treatment group and analysis center (ie, the imputation model will be the same as the analysis model).
3. Each complete data set will be analyzed with a logistic regression a factors of treatment group and analysis center.
4. Results from these analyses will be combined into a single inference.

